## 4.0 Study Endpoints (if applicable)

### Primary Outcome:

The primary outcome measure will be HADS, which is a conventional, validated, and widely used measure of psychosocial functioning. This scale consists of 14 items, seven of which contribute to a depression scale and seven that contribute to an anxiety scale. Therefore, three scores can be derived from this measure: an overall score, depression score, and anxiety score. The overall score will be used as the primary outcome measure and this measure will be administered at baseline, at each weekly psychosocial intervention session, post-treatment, and at 1-month follow up.

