**1.0 Objectives / Specific Aims**

The aim of this pilot project is to collect preliminary data on the feasibility, acceptance, and efficacy of an SLP-administered psychosocial intervention for people with post-stroke aphasia. The main objective of this pilot project is to determine whether the intervention is feasible and acceptable to participants with aphasia and their care partners, and we predict that it will be. Regarding the efficacy of intervention itself, we hypothesize that the psychosocial intervention will result in lower levels of psychosocial impairment (e.g., symptoms of anxiety and depression, chronic stress), better quality of life, and better retention and adherence to rehabilitation activities (i.e., attending therapies).

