### Secondary Outcomes:

Secondary measures of psychosocial functioning that are specifically validated for the aphasia population will be administered as well, including the D-VAMS, SASS, Stroke Aphasia Depression Questionnaire-10 (SADQ-10; Sutcliffe & Lincoln, 1998), Behavioural Outcomes of Anxiety Scale (BOA; Kneebone et al., 2012; Linley-Adams et al., 2014, Modified Perceived Stress Scale (mPSS; Hunting Pompon et al., 2018), Stroke Aphasia Quality of Life (SAQOL-39; Hilari et al., 2003), and Communication Confidence Rating Scale for Aphasia (CCRSA; Cherney et al., 2011; Babbitt et al., 2011). Most of these will be administered at baseline, post-treatment, and at 1-month follow-up (see below for a table with the timepoints for each measure and the rationale for inclusion). Two of these outcome measures will be also administered at the weekly sessions, including the D-VAMS and SASS.

A questionnaire related to attendance, retention and adherence to outpatient speech therapy services will also be collected at post-treatment to gather preliminary data on whether the psychosocial intervention was associated with good retention/in/adherence to rehabilitation activities. This will be done by administering a questionnaire to participants asking questions about whether they are receiving rehabilitation therapy, and if so, whether they have been attending and following recommendations.

Qualitative interviews will also be conducted at post-treatment and 1-month follow-up to aid in intervention refinement as well. Care partners of participants (e.g., family, friends, spouse) will be invited to participate in the interviews as well.

Table 1. Study Measures

Test Name	Construct	Timepoints	Justification
Primary			
Hospital Anxiety and Depression Scale (HADS)	Measures presence of signs/symptoms of depression and anxiety	All sessions	Overall assessment of psychosocial functioning
Secondary			
Dynamic Visual Analog Mood Scale (D-VAMS)	Measures mood based on reported feelings for 7 scales of emotion	All sessions	A weekly measure of mood fluctuations throughout the study
Simple Aphasia Stress Scale (SASS)	Measures perception of current stress level	All sessions	A weekly measure of acute stress

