Stroke Aphasia Depression Questionnaire-10 (SADQ-10)	Measures presence of signs/symptoms of depression in people with aphasia	Screening/Baseline, Post-treatment (Session 6), 1-month follow-up (Session 7)	Aphasia-validated measure of depression to compare with HADS outcome
Behavioural Outcomes of Anxiety Scale	Measures presence of signs/symptoms of anxiety	Screening/Baseline, Post-treatment (Session 6), 1-month follow-up (Session 7)	Aphasia-validated measure of anxiety to compare with HADS outcome
Modified Perceived Stress Scale (mPSS)	Measures perceived levels of stress in people with aphasia	Screening/Baseline, Post-treatment (Session 6), 1-month follow-up (Session 7)	Aphasia-validated measure of chronic stress to compare with other measures of psychosocial functioning

Stroke Aphasia Quality of Life (SAQOL-39)	Measures overall quality of life in people with aphasia	Screening/Baseline, Post-treatment (Session 6), 1-month follow-up (Session 7)	Aphasia-validated measure to examine whether intervention has an effect on quality of life
The Communication Confidence Rating Scale for Aphasia (CCRSA)	Measures how confident people with aphasia are at communicating in a range of scenarios	Screening/Baseline, Post-treatment (Session 6), 1-month follow-up (Session 7)	Aphasia-validated measure to examine whether intervention has an effect on communication confidence
Other Standardized Assessments			
Western Aphasia Battery-Revised (WAB-R)	Measures language abilities	Screening/Baseline	To determine eligibility for study and acquire language profile
Cognitive Assessment Scale for Stroke Patients	Measure cognitive abilities	Screening/Baseline	To examine relationships between cognition and primary/secondary outcome measures
Qualitative Assessments			
Rehabilitation Retention & Adherence	Measure whether they have been participating in rehabilitation activities and adhering to recommendations	Post-treatment (Session 6)	To determine whether psychosocial intervention may have had positive impact on rehabilitation retention/adherence
Participant and Care Partner Acceptability of Psychosocial Intervention	Measure participant and care partners' perceptions about psychosocial intervention	Post-treatment (Session 6), 1-month follow-up (Session 7)	To identify acceptability of the intervention by participants and their care partners and to refine intervention to meet patient needs

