## 12.0 Data Management

With 10 participants with aphasia, we are statistically powered to conduct feasibility analyses. For our primary quantitative analysis, we plan to conduct paired-samples *t*-tests to compare each outcome measure with 2 time points: baseline vs. post-treatment and baseline vs. 1-month follow-up. Baseline vs. post-treatment comparisons will be used to examine preliminary effects of the intervention on our primary outcome measures (HADS depression scores, HADS anxiety scores), and the secondary outcome measures listed above. Baseline vs. 1-month follow-up comparisons will be used to examine any delayed or maintained treatment effects on the primary and secondary outcome measures. Quantitative feasibility data and psychosocial data will also be examined descriptively given the small sample size.

Data gathered from the retention/adherence to speech therapy questionnaire and the semi-structured interview will also be analyzed descriptively and qualitatively for emergent themes that can be used to further refine and develop the psychosocial intervention.

To maintain participant confidentiality, all participants will be given a participant study ID which will be used on all their study documents and data. Participant names and direct identifiers will be stored separately from collected data and participant names and study IDs will be linked in one password-protected document saved on an MUSC Network computer or cloud-based storage account. Data will be stored in a secure data capture platform, on an MUSC Network computer or cloud-based storage account, and/or on paper in a locked file cabinet in a locked room on campus to which only research personnel have access. Interviews will be audio recorded and transcribed

for analysis. Audio recordings will be made on a Sony digital recorder and transferred as soon as possible after the session to an MUSC Network computer or a cloud-based storage account to which only research personnel have access. Once transferred, audio recordings will be deleted off the recording device. Consent forms will be stored separately from the data collected in a locked file cabinet in a locked room to which only relevant study personnel have access.

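### Section 4.0 makes the HADS overall score the primary outcome, but Section 12.0 names the HADS depression and anxiety scores as primary and never mentions the overall score

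*Combined protocol and SAP*

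**What the plan says.** Section 4.0, under Primary Outcome, notes that "three scores can be derived from this measure: an overall score, depression score, and anxiety score". It then chooses among them: "The overall score will be used as the primary outcome measure". The HADS is given at baseline, at each weekly intervention session, after treatment and at the 1-month follow-up.

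Section 12.0 (Data Management) contains the only statistical analysis text. It plans paired t-tests of every outcome measure, baseline against post-treatment and baseline against 1-month follow-up. The baseline to post-treatment tests are "to examine preliminary effects of the intervention on our primary outcome measures (HADS depression scores, HADS anxiety scores"; the parenthesis closes there and the secondary measures follow as a separate group. The overall score is not named anywhere in the section.

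Table 1 lists the HADS as the only primary measure without saying which score. Its justification reads "Overall assessment of psychosocial functioning". The secondary outcomes in Section 4.0 and Table 1 do not include the two HADS subscores.

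**The concern.** The endpoint section names one primary score. The analysis section names two, and neither is the one chosen in the endpoint section. An analyst who follows Section 4.0 reports one primary result per comparison. One who follows Section 12.0 reports two, with no statement of how to read them if only one improves. The subscores are primary under one section and have no stated role under the other.

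So the result presented as the pilot's primary efficacy estimate could be settled after the data are seen. Preliminary efficacy is a stated aim in Sections 1.0 and 10.0, and a reader of the eventual report could not tell which score had been chosen in advance.

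**Working it through.** **1. The passages side by side**

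| Place | What is primary | Overall score | Subscores |
|---|---|---|---|
| Section 4.0, Primary Outcome | One score | Named as primary | Mentioned as derivable, no role given |
| Section 4.0, Table 1 | HADS, no score named | Not specified | Not specified |
| Section 12.0 | Two scores | Not named | Named as primary |

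**2. Can any text reconcile them?**

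- *The general t-test plan in Section 12.0.* It covers every outcome measure, so the overall score may well be tested. That does not make it the primary score, because the same section gives that label to the subscores.
- *The HADS row of Table 1.* The word *overall* appears in the justification column and explains why the scale is used. It does not select a score.
- *The two aphasia-specific rows of Table 1.* The SADQ-10 is justified as "Aphasia-validated measure of depression to compare with HADS outcome" and the Behavioural Outcomes of Anxiety Scale as "Aphasia-validated measure of anxiety to compare with HADS outcome". A depression scale and an anxiety scale pair with the corresponding subscores at least as naturally as with the total, so these rows do not favour the overall score.

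Nothing resolves the conflict, and neither a redaction nor an amendment log accounts for it.

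**3. Could the choice change the result? (illustration)**

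The plan gives no alpha, effect size, standard deviation or correlation, so there is no figure of its own to reproduce. From the plan: 10 completers (Section 6.0) and paired t-tests (Section 12.0). Assumed: two-sided 5%, one comparison, equal standard deviation and equal true standardised change d in both subscores, and a correlation of 0.3, 0.5 or 0.7 between the subscore changes.

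A paired t-test is a one-sample t-test on the changes: t = mean change ÷ (SD of change ÷ √10), compared with the t distribution on 9 degrees of freedom. The overall change is the depression change plus the anxiety change. There were 200,000 simulated trials per setting (simulation standard error at most 0.0011). Each cell gives the three correlations in order.

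| d | Exactly one subscore significant | Overall result differs from *at least one subscore* |
|---|---|---|
| 0 | 0.091 / 0.085 / 0.072 | 0.074 / 0.061 / 0.045 |
| 0.3 | 0.209 / 0.183 / 0.145 | 0.125 / 0.100 / 0.074 |
| 0.5 | 0.351 / 0.299 / 0.235 | 0.156 / 0.126 / 0.100 |
| 0.8 | 0.397 / 0.337 / 0.260 | 0.096 / 0.090 / 0.081 |

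With no true change, the chance of a significant primary result is:

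- overall score: 0.050 at each correlation;
- at least one subscore: 0.095 / 0.093 / 0.086 (if independent, 1 − 0.95² = 0.0975);
- both subscores: about 0.004 / 0.008 / 0.014.

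If both subscores must be significant, the overall result differs from the subscore result in about 16–30% of trials at d = 0.5.

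**The case against.** The best opposing case accepts the mismatch but says it matters little.

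- *This is an uncontrolled pilot.* "The main objective of this pilot project is to determine whether the intervention is feasible and acceptable", the effects are called preliminary, and "Quantitative feasibility data and psychosocial data will also be examined descriptively given the small sample size". No alpha, success rule or go/no-go decision rests on a HADS score. **This stands** and limits the severity.
- *All the passages agree on the instrument.* The overall score and the subscores come from the same 14 items, so all three can be reported. **This stands** as far as data collection goes. The label of primary remains in dispute.
- *Section 4.0 chooses deliberately, while Section 12.0 has only a parenthesis, so Section 4.0 would naturally govern.* **This stands in part.** It is a good reason to prefer the overall score when correcting the text. But Section 12.0 is what an analyst will follow, and no text gives Section 4.0 precedence.
- *The missing rule for a split subscore result is not a separate fault, since the plan sets no success rule for any outcome.* **This stands.** The rule is needed only if the subscores are kept as primary.
- *The simulation rests on assumed inputs and treats significance as a verdict, which the plan does not do.* **This stands**, so the figures are illustrative. Requiring both subscores puts the null rate below 5%, so a raised false-positive rate is not a general consequence of the conflict. The same rule also makes disagreement with the overall score larger at d = 0.5.

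**Conclusion.** The concern holds. Sections 4.0 and 12.0 contradict each other on which HADS score is primary, and nothing else in the document decides between them. This is a textual conflict and depends on no calculation.

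Its consequence is modest. Under the stated assumptions, the overall-score result matches the at-least-one-subscore result in most trials; at d = 0.5 the two differ in 10–16%. With no true change, the chance of a significant primary result is 5.0% for the overall score, 8.6–9.5% if either subscore counts, and about 0.4–1.4% if both must be significant. The size and even the direction of the effect depend on a rule that the plan does not state. It should be fixed, but it does not threaten the feasibility objective.

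**What to change.** Before any data are analysed:

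1. In Section 12.0, replace the two subscores in the parenthesis with the HADS overall score, following the explicit choice in Section 4.0.
2. In Sections 4.0 and 12.0, list the HADS depression score and the HADS anxiety score as secondary outcomes. They then remain available to set beside the SADQ-10 and the anxiety scale, as Table 1 suggests.

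If the sponsor does intend the two subscores as primary, change the sentence in Section 4.0 instead, give the overall score a secondary role, and state whether one or both must improve.

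An optional clarification, not a correction: label baseline against post-treatment as the primary comparison and baseline against 1-month follow-up as secondary, in line with the roles Section 12.0 already describes.

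The cost is one changed parenthesis and one added line in each of the two sections, with no new data, visits or participants. The downside is that fewer results can be presented as primary.

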### Secondary Outcomes:

Secondary measures of psychosocial functioning that are specifically validated for the aphasia population will be administered as well, including the D-VAMS, SASS, Stroke Aphasia Depression Questionnaire-10 (SADQ-10; Sutcliffe & Lincoln, 1998), Behavioural Outcomes of Anxiety Scale (BOA; Kneebone et al., 2012; Linley-Adams et al., 2014, Modified Perceived Stress Scale (mPSS; Hunting Pompon et al., 2018), Stroke Aphasia Quality of Life (SAQOL-39; Hilari et al., 2003), and Communication Confidence Rating Scale for Aphasia (CCRSA; Cherney et al., 2011; Babbitt et al., 2011). Most of these will be administered at baseline, post-treatment, and at 1-month follow-up (see below for a table with the timepoints for each measure and the rationale for inclusion). Two of these outcome measures will be also administered at the weekly sessions, including the D-VAMS and SASS.

A questionnaire related to attendance, retention and adherence to outpatient speech therapy services will also be collected at post-treatment to gather preliminary data on whether the psychosocial intervention was associated with good retention/in/adherence to rehabilitation activities. This will be done by administering a questionnaire to participants asking questions about whether they are receiving rehabilitation therapy, and if so, whether they have been attending and following recommendations.

Qualitative interviews will also be conducted at post-treatment and 1-month follow-up to aid in intervention refinement as well. Care partners of participants (e.g., family, friends, spouse) will be invited to participate in the interviews as well.

Table 1. Study Measures

Test Name	Construct	Timepoints	Justification
Primary			
Hospital Anxiety and Depression Scale (HADS)	Measures presence of signs/symptoms of depression and anxiety	All sessions	Overall assessment of psychosocial functioning
Secondary			
Dynamic Visual Analog Mood Scale (D-VAMS)	Measures mood based on reported feelings for 7 scales of emotion	All sessions	A weekly measure of mood fluctuations throughout the study
Simple Aphasia Stress Scale (SASS)	Measures perception of current stress level	All sessions	A weekly measure of acute stress
Stroke Aphasia Depression Questionnaire-10 (SADQ-10)	Measures presence of signs/symptoms of depression in people with aphasia	Screening/Baseline, Post-treatment (Session 6), 1-month follow-up (Session 7)	Aphasia-validated measure of depression to compare with HADS outcome
Behavioural Outcomes of Anxiety Scale	Measures presence of signs/symptoms of anxiety	Screening/Baseline, Post-treatment (Session 6), 1-month follow-up (Session 7)	Aphasia-validated measure of anxiety to compare with HADS outcome
Modified Perceived Stress Scale (mPSS)	Measures perceived levels of stress in people with aphasia	Screening/Baseline, Post-treatment (Session 6), 1-month follow-up (Session 7)	Aphasia-validated measure of chronic stress to compare with other measures of psychosocial functioning

Stroke Aphasia Quality of Life (SAQOL-39)	Measures overall quality of life in people with aphasia	Screening/Baseline, Post-treatment (Session 6), 1-month follow-up (Session 7)	Aphasia-validated measure to examine whether intervention has an effect on quality of life
The Communication Confidence Rating Scale for Aphasia (CCRSA)	Measures how confident people with aphasia are at communicating in a range of scenarios	Screening/Baseline, Post-treatment (Session 6), 1-month follow-up (Session 7)	Aphasia-validated measure to examine whether intervention has an effect on communication confidence
Other Standardized Assessments			
Western Aphasia Battery-Revised (WAB-R)	Measures language abilities	Screening/Baseline	To determine eligibility for study and acquire language profile
Cognitive Assessment Scale for Stroke Patients	Measure cognitive abilities	Screening/Baseline	To examine relationships between cognition and primary/secondary outcome measures
Qualitative Assessments			
Rehabilitation Retention & Adherence	Measure whether they have been participating in rehabilitation activities and adhering to recommendations	Post-treatment (Session 6)	To determine whether psychosocial intervention may have had positive impact on rehabilitation retention/adherence
Participant and Care Partner Acceptability of Psychosocial Intervention	Measure participant and care partners' perceptions about psychosocial intervention	Post-treatment (Session 6), 1-month follow-up (Session 7)	To identify acceptability of the intervention by participants and their care partners and to refine intervention to meet patient needs

## 5.0 Inclusion and Exclusion Criteria/ Study Population

**People with aphasia:** People with aphasia will be screened for eligibility through an in-person meeting with a member of the research team after written consent is obtained. Screening will consist of administration of a questionnaire, language assessment, and review of medical records. Medical records will be reviewed to confirm left-hemisphere stroke, time post-stroke, and the absence of other neurological disorders (an exclusion criterion). Medical records will be accessed via Epic if the participant was treated at MUSC for their stroke or requested from their admitting hospital. If the participant is judged to not meet all inclusion/exclusion criteria, they will not be allowed to continue with the remainder of the study.

### ***Inclusion Criteria***

- 18-81 years old

- Native English speaker (English fluency by age 7)
- Aphasia as a result of a left-hemisphere ischemic or hemorrhagic stroke (WAB-R Aphasia Quotient < 93.8)
- At least 1-month post-stroke
- Confirmation of left hemisphere stroke per medical records
- Discharged from hospital
- Participant is willing and able to consent for themselves.

### ***Exclusion Criteria***

- Uncorrected hearing or visual impairment that prevents completion of experimental activities as determined by self-report
- History of other neurological disorder or disease beside stroke (e.g., dementia, traumatic brain injury) as determined by self-report and/or medical records
- Self-reported history of premorbid learning disability
- Severe auditory comprehension deficits (as indicated by a score of more than two standard deviations below norms on the Auditory Verbal section of WAB-R)

**Care partners:** Care partners of included participants with aphasia will be invited to participate in the post-treatment and follow-up qualitative interviews to get their perspectives on the intervention and its feasibility. If the participant with aphasia does not have an involved care partner, then no care partner will be included in the interviews.

### ***Inclusion Criteria***

- 18+ years old
- Care partner of an included participant with aphasia (e.g., close friend or family member that had frequent interactions with the participant during their participation in the study).

***Exclusion Criteria*** – None.

Efforts will be made to ensure a representative sample of the broader Charleston area in terms of sex/gender and race/ethnicity, however, participants will not be excluded based on sex/gender or race/ethnicity, thus there is potential for an imbalance.

Children will be excluded because stroke in children is rare and presentation of language symptoms is different compared to adults due to brain plasticity and the course of language development.

